SSP	Peer Health Educator deliver 8 two hour group sessions that are approximately 1 week apart focused on teaching effective, concrete cognitive and behavioral skills.	PHE's need to be TWOC and deliver the intervention. The intervention needs to be condensed to 8 sessions maximum for TWOC to complete the entire program. After reviewing the content of all of the SSP sessions, the team decided on the following sessions: 1) Prioritizing Safety, 2) Understanding trauma and PTSD; 3) Getting support from yourself and others; 4) Taking care of your whole self; 5) Knowing your triggers and how to handle them; 6) Setting boundaries in relationships; 7) Healthy relationship beliefs; 8) Review game and Graduation. Sessions will also be adapted to include gender-based violence, and gender affirmation.				
Individual-	Level Peer Navigation					
HIV Peer Services	One-to-one navigation to help link people to healthcare systems and identify and reduce barriers to care. Navigation services also include working together to create an individualized health behavior change plan.	PHE's who are also TWOC need to deliver the navigation services, which is key to building trust and safety planning based on shared experience. PHE's will need to provide assistance with identifying trans-friendly HIV prevention and care services, as well as gender affirmation services (e.g., name changes, hormones). Individualized health behavior change plans will also identify and work to address barriers to reducing HIV transmission risk (e.g., violence from dates) and engagement in HIV services.				

VI. Study Team Experience

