6. Integration	Adaptation and Training	Analyze data to refine manuals and develop training materials			
7. Training		Generate training manual and conduct training with PHE			
8. Testing	RCT	Conduct one-arm pilot.			

VII-1. Intervention Overview

The *TSoCP SSP* intervention (referred to as "*Kickin' it with the Gurlz*" with participants and in intervention materials) includes 8 weekly group sessions focused on topics related to

understanding trauma and PTSD, healing from trauma, and taking care of your health and wellbeing. Each group session will be co-facilitated by two PHEs who identify as transgender women of color, and will include up to 12 transgender women of color participants. Each group session will last 2 hours. (See Appendix XII-1. Group Sessions Manual). In addition to group sessions, participants will have 1-on-1 sessions with a PHE as part of the intervention. 1-on-1 intervention sessions will focus on identifying health-related needs and linking participants to affirming healthcare referrals and community resources, as well as individualized follow-up from group sessions (see Appendix Y. Resource and Referral List). During enrollment visit study procedures, participants will complete a Violence and Gender Affirmation Screener (see Appendix XII-3. Violence & Gender Affirmation Screener) that PHEs will access that collects participant needs related to violence and safety as well as medical and legal gender affirmation; additional needs and priorities will be assessed through conversation. The first introductory 1-on-1 session will occur before the start of group sessions. Participants have the choice of attending optional additional 1-on-1 sessions with a PHE during the 8 weeks they are attending group sessions, up to once a week.

VII-2. Assessing Acceptability and Feasibility

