To assess feasibility, we will monitor rates of outreach, recruitment, eligibility, enrollment. attendance, retention, and assessment completion. PHEs will complete a structured "intervention log" after each session to assess fidelity to intervention, time needed, and feasibility of delivering the intervention curriculum as designed (see Appendix XII-4. Intervention Log). To assess acceptability, we will use a modified version of the Client Satisfaction Questionnaire (see Appendix XII-5. Adapted Client Satisfaction Questionnaire), which participants will complete at the end of each group and individual session. We will also assess acceptability using data on participants' reactions to various program components gathered from PHEs "intervention logs". We will also explore the feasibility and acceptability of verifying HIV care engagement and viral load data by asking participants to sign releases to contact their provider and/or clinic for verification of their self-reported health care behaviors. Feasibility will be evaluated by monitoring staff hours required to verify data and rates of verifiable engagement reports. Acceptability of our verification methods by participants will be assessed by rates of agreement to provide consent to contact providers (90% or higher will be considered acceptable) and will be explored during exit interviews with participants and staff. Finally, we will conduct 30-minute exit interviews at the conclusion of the program with both participants and program staff to gather qualitative feedback about the structure, content, and experience of the intervention. Participant exit interviews will also explore barriers to RCT designs and implementation. (See Appendix XII-6. Exit Interview Guide – Participants, Appendix XII-7. Exit Interview Topic Guide - Program Staff).

VIII. Study Procedures

VIII-1. COVID-19 Safety

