additional individual sessions throughout the intervention period (through the end of the group sessions), up to once a week. Individual sessions may be delivered in-person in a private space at the Ruth Ellis Center, by phone, or by Zoom. Mode of contact/interaction for individual sessions will be dependent on current guidelines and approvals related to COVID-19; if/when in-person research activities are not permitted, all sessions will be virtual and occur by Zoom or phone. If/when in-person research activities are allowed, then PHEs will defer to the participant's preference. Regardless of the location/format of individual sessions, PHEs will ensure they are in a location that maintains the participant's privacy. PHEs may follow up with participants in between individual sessions to facilitate referrals and connection to community resources. (See Appendix XII-16. Individual Sessions Guide, and Appendix XII-2. Individual Session Resources and Referrals List.)

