VIII-5.2 Group sessions. After all participants in one group cohort have been enrolled and had an initial individual session with their PHE, weekly group sessions will commence. Group sessions will include participants in this study, as well as another study our research team has running concurrently, "A multicomponent intervention to address gender-based violence in HIV prevention for women: Phase 2" (HUM00190671); that study involves testing the feasibility, acceptability, and initial efficacy of the TSoCP SSP intervention on engagement in the HIV prevention continuum of care and mental health outcomes among transgender women who are HIV negative or have an unknown HIV status in the Detroit Metro Area. Group sessions will be held once a week for eight weeks (see Appendix XII-1. Group Sessions Manual). Group sessions will either occur in-person in a private room at Ruth Ellis Center or virtually via Zoom. depending on current guidelines and restrictions related to COVID-19. It is possible that due to inclement weather or an emergency situation, session(s) may need to be rescheduled. In this event, a group session may be rescheduled for a later time that week or postponed to the following week; if a session is postponed by one week, this would delay the end of the intervention (as well as follow up assessments and exit interview) by one week. Participants will be encouraged to attend all group sessions; however, if a participant misses session(s), she will still be allowed to remain in the intervention and attend future sessions. If a participant misses a group session, whenever feasible, she will be offered the opportunity to review the group session content with a PHE in an individual session before the next group.

VIII-6. Follow Up Visits

The preferred timeframe for all follow-ups is within 14 days prior to or 28 days after the target study visit date. If the participant is unable to complete the necessary study procedures within this timeframe, study staff will work with the participant to identify a day as soon as possible to complete the procedures. Scheduling of study procedures will not be recalibrated based on the actual date that the study procedures were completed. The exit interview, immediate-, and 1-month post-intervention follow-up assessment must be based on the elapsed time from the date of final session completion.

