VIII-5.1 Exit Interview. After completion of the final group session, participants will complete a brief in-depth interview about their experiences with the intervention to further assess acceptability and generate strategies for conducting research and RCTs with similar communities. Exit interviews with participants will be conducted by the study RA or Project Director, will last approximately 30 minutes, and will be audio-recorded. Exit interviews may occur in-person at the Ruth Ellis Center, by phone, or by Zoom (See Appendix XII-6. Exit Interview Guide – Participants).

VIII-5.2 Post-Intervention Follow Up Survey. After completion of the final group session, participants will receive a link to complete a follow up survey on Qualtrics. The follow up survey will take approximately 30 minutes to complete. If in person, the Qualtrics survey may be completed on a study tablet; otherwise the participant will receive a link to complete the survey on her own personal device.

VIII-5.3 1-Month Post-Intervention Follow Up Survey. One month after the final group session, participants will receive a link to complete a second and final follow up survey on Qualtrics. The follow up survey will take approximately 30 minutes to complete. If in person, the Qualtrics survey may be completed on a study tablet; otherwise the participant will receive a link to complete the survey on her own personal device.

VIII-7. Participant Incentives

To incentivize participation, participants in the one-arm trial will receive \$40 for baseline, \$35 for immediate post-intervention, and \$50 for the 1-month post-interventions follow-up surveys, as well as \$20 for attending each group session and completing an exit interview. Incentives will be provided in the form of a gift card. Participants will also be compensated for their travel for assessments (transportation provided through Uber or Lyft or a \$20 gas card) and intervention sessions that are conducted in person, and provided a meal at in-person group sessions. To receive an incentive, participants will complete a brief incentive survey programmed into Qualtrics. (See Appendix XII-14. Incentive Survey.)

VIII-8. Retention Strategies

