Our team has extensive experience in retaining transgender women of color in research studies. Much of our success can be attributed to our community-engaged approach to research efforts, including TSoCP serving our community partners located at the Ruth Ellis Center, which provides services for young adults and is in close proximity to Corktown Health Center, which provides healthcare services for all study participants regardless of age. Using these methods, our prior studies with transgender women of color have regularly yielded follow-up rates above 80%-90%. We will apply our rigorous multi-pronged approach to ensure high rates of follow-up.

Study staff are trained to emphasize several times throughout the enrollment process that it is critical that we be able to reach participants for follow-up. Participants will complete a detailed Locator Form with multiple methods of contact information after consenting to be in the study, which will aid in follow up. Staff will inquire about and update any changes to contact information at each study visit. We also request that participants inform study staff if any of their contact information changes. Participants are told that it is important that we reach them to see how they are doing, regardless of whether they respond to the intervention components, whether or not they engage in HIV care, whether or not they are doing well or poorly; that their participation in the study could increase scientific knowledge about whether this program is meaningful to the community; that their research information will be confidential; and that we are grateful for their contribution to the study. When participants are seen in-person, they will be given [name] business card, which is filled in with their approximate follow-up appointment date and the incentive amount.

Follow-up status and challenges will be routinely reviewed at weekly staff meetings. If follow-up rates fall, we will use a proactive management approach to identify the root source of the challenges and troubleshoot potential solutions. This may include meetings with our CAB to brainstorm solutions or modifying procedures.

IX. Data Collection and Management

IX-1. Data Collection Methods

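### The only participant-completed satisfaction score described is collected at attended sessions, so women who stop early contribute no end-of-program rating

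*Protocol*

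**What the plan says.** Acceptability is a named objective of this one-arm pilot of 30 women (Protocol, III and IV-2). Section VII-2 lists how the acceptability of the intervention is assessed:

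- An adapted Client Satisfaction Questionnaire, "which participants will complete at the end of each group and individual session". No other time point is described for it.
- Participants' reactions as recorded in the intervention logs, which the peer health educators write after each session.
- Exit interviews at the end of the program, which are qualitative. Under IX-2 their recordings are stored without the study ID.

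On the sessions that generate forms, VII-1 says: "The first introductory 1-on-1 session will occur before the start of group sessions". Eight weekly group sessions follow. Section VIII-5.1 (1-on-1 Sessions) lets each woman choose how often to have "additional individual sessions throughout the intervention period (through the end of the group sessions), up to once a week".

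Partial attendance is expected. VIII-5.2 (Group sessions) says that "if a participant misses session(s), she will still be allowed to remain in the intervention and attend future sessions". Table 1 shows that completion was already a worry: "The intervention needs to be condensed to 8 sessions maximum for TWOC to complete the entire program".

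A survey at program end already exists. VIII-5.2 (Post-Intervention Follow Up Survey) says: "After completion of the final group session, participants will receive a link to complete a follow up survey on Qualtrics". The protocol text names no satisfaction measure in it; its content is in Appendix XII-8, which is not shown.

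**The concern.** Under this schedule, being asked for a rating depends on having come. A woman who attends two group sessions and then stops gives a few ratings, all made before she stopped. A woman who enrols but never has the introductory session gives none. What either would say about the program as a whole at its end is not scored.

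If women who stop tend to be less satisfied, the satisfaction result will look better than the enrolled group would report. If they stop for other reasons, such as the length of the program, it need not. The last forms of women who stopped can be compared with those of women who continued, but such forms cannot show a view that was formed at or after stopping.

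The pilot is meant to lay the groundwork for a larger trial, so the views of women who did not stay are among the more useful things it can learn. When, and from whom, a rating is requested is fixed by the protocol. An analysis plan can average forms within woman, but it cannot recover a rating that was never requested.

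**Working it through.** The protocol states no satisfaction figure or threshold, so there is nothing to reproduce. The check has four steps.

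**1. Forms per enrolled woman.** Minimum 0, because the introductory session comes after enrollment and may not take place. Maximum 1 introductory + 8 group + 8 optional weekly individual = 17.

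**2. Do the other listed sources give an end-of-program score from everyone?**

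| Source (VII-2) | Completed by | When | Quantitative end rating from all enrolled? |
|---|---|---|---|
| Session questionnaire | Participant | Each attended session | No |
| Intervention log | Staff | Each session | No |
| Exit interview | Participant | End of program | No (qualitative; recordings not linked to study ID) |

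Attendance and retention are also monitored, but as feasibility measures. They show that a woman stopped, not what she thought.

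**3. Possible size.** Let L of the 30 women stop, each having given at least one form. Let c be the share of those L who rated favourably while attending but would not do so at the end. With one summary per woman, the share satisfied is overstated by

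L × c / 30.

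| L | c = 0 | c = 25% | c = 50% |
|---|---|---|---|
| 3 | 0 | 2.5 points | 5 points |
| 6 | 0 | 5 points | 10 points |
| 9 | 0 | 7.5 points | 15 points |

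L and c are assumptions; the protocol gives neither. If a share g of the women who stop would move the other way, the result becomes L × (c − g) / 30, which can be zero or negative.

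A second illustration uses different assumptions. Suppose 90% of women who stay are satisfied, 6 of 30 (20%) stop, and 30%-70% of those who stop are satisfied. Ratings from the late sessions then overstate the all-enrolled figure by 0.20 × (0.90 − 0.70) = 4 points to 0.20 × (0.90 − 0.30) = 12 points.

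**4. What an end rating would recover.** VIII-8 reports follow-up above 80%-90% in prior studies. At those rates 24-27 of 30 respond and 3-6 do not, so best-to-worst-case bounds are 3/30 = 10 to 6/30 = 20 points wide. With L = 6:

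- Non-response unrelated to stopping: 6 × 0.8 = 4.8 to 6 × 0.9 = 5.4, or about 5 of the 6 recovered.
- All non-responders are women who stopped: 6 − 6 = 0 to 6 − 3 = 3 recovered.

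**The case against.** The strongest reply has four parts.

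*The appendices are not shown.* Appendix XII-8 (survey measures) or XII-5 (the adapted questionnaire) may already contain an end-of-program item. That stands. A reader might infer that no such rating is collected at all; the document does not support that. What can be said is that VII-2, which sets out the acceptability measures, does not list one.

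*Late views have a planned route.* The exit interview is held at program end in person, by phone or by Zoom. It is paid and carries no stated attendance requirement. That also stands. In a pilot of 30, asking a woman why she stopped is a sensible way to find out, and leaving the study ID off the recording prevents linkage, not collection. But the interview gives no score to set beside the session ratings.

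*The follow-up survey already reaches women who stopped.* A reader might infer that the survey timing is ambiguous, because VIII-6 says follow-ups "must be based on the elapsed time from the date of final session completion" without saying whose final session is meant. The rest of the document largely answers this. VIII-5.2 (Group sessions) says that postponing a group session by a week moves the follow-up assessments by a week. VIII-5.1 ends the intervention period with the group sessions. VIII-5.3 sends the second survey a month after the final group session with no attendance condition. VIII-8 stresses reaching women whether or not they respond to the intervention. Follow-up thus runs on the cohort's schedule, and the timing is not a fault. This helps the remedy: the vehicle is already in place.

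*The size is assumed.* L and c are invented, c = 0 gives zero, and no satisfaction threshold depends on the result. A reader might infer that the score will be too favourable; the document does not establish a direction. The remedy could also recover least where it matters most, if non-responders are the women who stopped. All of this limits the weight of the point. It does not remove the dependence of the score on attendance.

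Session forms also have a merit of their own: they capture ratings before a woman stops, which an end-only score could lose. They should stay.

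**Conclusion.** The point holds as a modest improvement to the design. The one participant-completed satisfaction score described in VII-2 depends on attendance, and no listed acceptability source is a quantitative end-of-program rating sought from all enrolled women. The satisfaction result may therefore differ from what the full group of 30 would report. The central illustration is 5-10 points, and it rests wholly on assumed values for how many stop and how many would change their rating. Confidence is medium, mainly because Appendix XII-8 is not shown. How the session forms are combined is a matter for the analysis plan and is not part of this point.

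**What to change.** Keep the session forms and the exit interviews as they are. Then:

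- Add a short overall satisfaction rating to the existing post-intervention survey. If Appendix XII-8 already has one, name it in VII-2 as an acceptability measure.
- State that it goes to every enrolled woman who has not withdrawn, whatever her attendance, at her cohort's final group date. The follow-up schedule already implies this.
- Report it with all enrolled women as the denominator, showing non-responders and withdrawals, beside attendance and the session ratings.

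The cost is a few extra items in a 30-minute survey that is already paid for separately from group attendance, plus a small amendment. Exit-interview privacy is unchanged. The residual non-response may be concentrated in women who stopped, which is why the denominator and the non-responders need to be visible.
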